#### **8.5.6 Safety Monitoring for LDL-C Elevations**

Beginning at Week 13, laboratory alerts will be in place to notify the Investigator if a patient has an LDL-C > 160 mg/dL on 2 consecutive visits. If this occurs, LDL-C values for this patient will be unblinded for the remainder of the study and the Investigator will be encouraged to initiate/adjust treatment to lower LDL-C according to country-specific guidelines (e.g., initiate statin therapy, increase the statin dose for patients who are already on treatment, add ezetimibe if on maximal statin therapy).

#### **8.5.7 Safety Monitoring for Hypoglycemia**

##### **Classification of Hypoglycemia**

###### **Alert value for hypoglycemia**

≤ 70 mg/dL (≤ 3.9 mmol/L) plasma concentration

###### **Severe Hypoglycemia**

Requires assistance of another person to actively administer carbohydrates, glucagon, or take other corrective actions. Plasma glucose concentrations may not be available during an event. Neurological recovery following plasma glucose levels returning to normal considered sufficient evidence that event was induced by low plasma glucose concentration

###### **Documented Symptomatic Hypoglycemia**

Typical hypoglycemia symptoms accompanied by measured plasma glucose ≤ 70 mg/dL (≤ 3.9 mmol/L)

###### **Asymptomatic Hypoglycemia**

Not accompanied by typical hypoglycemia symptoms but with measured plasma glucose ≤ 70 mg/dL (≤ 3.9 mmol/L)

### Probable Symptomatic Hypoglycemia

Typical hypoglycemia symptoms not accompanied by plasma glucose determination but likely caused by plasma glucose  $\leq 70$  mg/dL ( $\leq 3.9$  mmol/L)

In the event of an episode of symptomatic documented hypoglycemia (FPG  $< 70$  mg/dL), if the patient is on insulin, the Investigator shall reduce the total daily dose by 5-15%. If the patient is on oral ant-diabetic drugs, the Investigator should use his or her discretion regarding changes to the drug regimen to help prevent future incidences of hypoglycemic events. In all cases, the adjustments made to medication should be carefully documented via electronic diary (insulin) and/or concomitant medication CRF.

A **documented severe hypoglycemic event** is defined as one in which the patient requires assistance of another person to obtain treatment for the event and has a plasma glucose level  $\leq 70$  mg/dL ( $\leq 3.9$  mmol/L). The rescue treatment of hypoglycemia may include IV glucose or buccal or intramuscular glucagon.

The definition of severe symptomatic hypoglycemia includes all episodes in which neurological impairment was severe enough to prevent self-treatment and which were thus thought to place patients at risk for injury to themselves or others. Note that “requires assistance” means that the patient could not help himself or herself. Someone being kind that assists spontaneously the patient when not necessary does not qualify as “requires assistance.”

Severe hypoglycemia will be qualified as a SAE only if it fulfills SAE criteria.

If a patient presents with symptoms of hypoglycemia, the Investigator will need to take immediate action to confirm the patient’s glucose level and treat the patient accordingly.

Patients must be instructed on the monitoring and management of hypoglycemic episodes at the Baseline Visit.

The experience of hypoglycemia may vary greatly from patient to patient. However, there are certain classical signs and symptoms, of which patients should be aware as a clue that their blood glucose may be low. Common symptoms include headache, heart pounding, confusion, disorientation, numbness or tingling, pale skin, shakiness or tremulousness, increased appetite, anxiousness or nervousness, lightheadedness or dizziness, sweating, and weakness. Coma could occur if blood sugar correction is not performed.

If patients suspect they might be having a hypoglycemia reaction, they should check their blood glucose using their meters as soon as possible, before treatment if possible, provided they feel it is safe to do so. If there is doubt about safety they should treat the event first, using some sugar, milk, or juice for example, then obtain and record a blood glucose value as soon as possible thereafter. The time and nature of treatment should be noted, and especially if any blood glucose result was before or after treatment. It would be helpful for the patient to note if a contributory factor (e.g., missed or reduced meals, unaccustomed physical activity) occurred earlier in the day of the event.

Instructions should be provided to all patients on the appropriate use of a glucose meter.

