## STUDY DESIGN AND TREATMENT SCHEMA

## STUDY GLOSSARY

Abbreviation	Definition
2'-MOE	2'-O-(2-methoxyethyl)
AE	adverse event
AGL	acquired generalized lipodystrophy
ALT	alanine aminotransferase (SGPT)
ANA	antinuclear antibody
ANCOVA	analysis of covariance
APL	acquired partial lipodystrophy
[REDACTED]	[REDACTED]
[REDACTED]	[REDACTED]
apoC-III	apolipoprotein C-III
apoE	apolipoprotein E
aPTT	activated partial thromboplastin time
ASO	antisense oligonucleotide
AST	aspartate aminotransferase (SGOT)
BMI	body mass index
BP	blood pressure
BUN	blood urea nitrogen
CBC	complete blood count
CGL	congenital generalized lipodystrophy
CT	computed tomography
[REDACTED]	[REDACTED]
DSMB	Data and Safety Monitoring Board
ECG	electrocardiogram
eCRF	electronic Case Report Form
EDC	electronic data capture
ET	early termination
FAS	full analysis set
FPG	fasting plasma glucose
FPL	familial partial lipodystrophy
FSH	follicle-stimulating hormone
GCP	Good Clinical Practice
GLP-1	glucagon-like peptide 1
HAV	hepatitis A virus

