#### **6.2.7 Self-monitoring Blood Glucose**

A calibrated glucometer will be distributed to patients with diabetes at least 1 week before dosing, for their home-based glucose monitoring (Self-Monitoring Blood Glucose [SMBG]). Fasting SMBG will be self-measured in the morning: daily if the patient is on insulin therapy, and weekly if on oral antidiabetic therapy. Training on the use of the glucometer will be provided before dosing. The SMBG may start at the beginning of the diet run-in period continuing to the end of the post-treatment follow-up period.

[REDACTED]

Subjects who use a glucometer should bring their glucometer to every clinic visit. The Investigator or delegate will review the glucometer printout at every clinic visit to evaluate if self-monitored plasma glucose values exceed threshold values as per the Safety Monitoring for either Hypoglycemia or Hyperglycemia sections ([Sections 8.5.7](#) and [8.5.8](#), respectively).

All diabetic patients will note any changes in their insulin dose and/or oral antidiabetic therapy, as well as any hypoglycemic or hyperglycemic episodes they may experience. Diabetic patients on insulin should enter their insulin into their diary daily.

The Investigator or delegate will ask patients at every clinic visit if they made changes in their insulin dose or oral antidiabetic therapy, and if they experienced a hypoglycemic or hyperglycemic episode.

- Patients will be instructed on the monitoring and management of hypoglycemic and hyperglycemic episodes at each visit
- Documented symptomatic hypoglycemic episodes should be captured as adverse events in the adverse event CRF. Documented symptomatic hypoglycemia is defined as typical hypoglycemia symptoms accompanied by measured plasma glucose  $\leq 70$  mg/dL ( $\leq 3.9$  mmol/L). Should a subject require assistance of another person to actively administer carbohydrates, glucagon, or take other corrective actions, this should be recorded as treatment for the adverse event on the AE CRF and documented in the source
- Any changes in insulin dose or oral antidiabetic therapy should be captured into the Concomitant Medication CRF

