### **8.5.8 Monitoring Rule for Documented Hyperglycemia**

Routine fasting SMBG and central lab alerts on FPG (and HbA1c after Week 12) are set up to ensure that glycemic parameters remain under predefined thresholds values. If one fasting SMBG value exceeds the specific glycemic limit on 1 day, the patient checks it again during the 2 following days. If all the values in 3 consecutive days exceed the specific limit, the patient should contact the Investigator and a central laboratory FPG measurement (and HbA1c after Week 12) is performed.

The threshold values are defined as follows, depending on study period:

- From Baseline visit to Week 12 (including value at Week 12) of Randomized Treatment period or OLE period:
  - FPG > 300 mg/dL (16.6 mmol/L)
- From Week 12 to Week 24 (including value at Week 24) of Randomized Treatment period or OLE period:
  - FPG > 270 mg/dL (15.0 mmol/L) or
  - HbA1c > 9.5% (for patients with Baseline HbA1c < 8%) and HbA1c increase of more than 1.5% from Baseline (for patients with Baseline HbA1c ≥ 8%)
- From Week 24 up to Week 52 of Randomized Treatment period or OLE period:
  - FPG > 240 mg/dL (13.3 mmol/L) or
  - HbA1c > 9.5% (for patients with Baseline HbA1c < 8%) and HbA1c increase of more than 1.5% from Baseline (for patients with Baseline HbA1c ≥ 8%)

In case of FPG/HbA1c above the threshold values, the Investigator should ensure that no reasonable explanation exists for insufficient glucose control and in particular that:

- Plasma glucose was actually measured in the fasting condition
- Absence of intercurrent disease which may jeopardize glycemic control. In case of an emergency (e.g., surgery, infection), the Investigator can take appropriate measures for glycemic control. If the measure does not exceed 7 days, then it will not be considered a rescue. If the measure lasts beyond 7 days then it will be treated as a rescue
- Compliance to treatment is appropriate
- Compliance to diet and lifestyle is appropriate

If any of the above can reasonably explain the insufficient glycemic control, the Investigator should undertake appropriate action, i.e.:

- Investigation and treatment of intercurrent disease (to be reported in AE/concomitant medication parts of the eCRF)
- Stress on the absolute need to be compliant to treatment

- Organize a specific interview with a Registered Dietician or other qualified nutrition professional and stress on the absolute need to be compliant to diet and lifestyle recommendations

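### The mandatory insulin reduction in Protocol 8.5.7 is triggered by a fasting glucose below 70 mg/dL, although the protocol defines the same event by any measured glucose at or below 70 mg/dL

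*Protocol*

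**What the plan says.** Protocol 8.5.7 sets a glucose limit for hypoglycemia in several places. The alert value is "≤ 70 mg/dL (≤ 3.9 mmol/L) plasma concentration". Documented symptomatic hypoglycemia is "Typical hypoglycemia symptoms accompanied by measured plasma glucose" at or below 70 mg/dL (3.9 mmol/L). Section 6.2.7 repeats this for adverse event recording: "Documented symptomatic hypoglycemia is defined as typical hypoglycemia symptoms accompanied by measured plasma glucose" at or below the same limit. None of these carries a fasting condition.

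The action paragraph of 8.5.7, placed after the definition of probable symptomatic hypoglycemia, begins "In the event of an episode of symptomatic documented hypoglycemia (FPG" and completes the parenthesis with a strict limit of below 70 mg/dL. If the patient is on insulin, "the Investigator shall reduce the total daily dose by 5-15" percent. For oral anti-diabetic drugs, the same paragraph leaves any change to the investigator's discretion.

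The Study Glossary expands FPG as "fasting plasma glucose".

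**The concern.** The action sentence names the event that the protocol has already defined, but attaches a different test to it. The test differs in two ways: it asks for a fasting measurement, and it replaces at or below 70 with below 70.

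This is an operative safety threshold, because it decides when an insulin reduction is compulsory. Symptomatic lows can occur at any time of day. If the trigger is applied as written, those outside the fasting state are recorded as adverse events without requiring a dose change. If another site treats the parenthesis as shorthand for the defined term, the same event does require one. Sites could therefore handle identical events differently.

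**Working it through.** No power, alpha or sample-size figure is involved. The check sets the texts side by side and then does two short calculations.

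**1. The limits compared**

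| Place in protocol | Measurement | Limit | Fasting required? |
|---|---|---|---|
| 6.2.7, documented symptomatic event | measured plasma glucose | ≤ 70 mg/dL (≤ 3.9 mmol/L) | no |
| 8.5.7, alert value | plasma concentration | ≤ 70 mg/dL (≤ 3.9 mmol/L) | no |
| 8.5.7, documented symptomatic event | measured plasma glucose | ≤ 70 mg/dL (≤ 3.9 mmol/L) | no |
| 8.5.7, documented severe event | plasma glucose | ≤ 70 mg/dL (≤ 3.9 mmol/L) | no |
| 8.5.7, trigger for insulin reduction | FPG | < 70 mg/dL, no mmol/L value | yes |

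The last row is the only one that differs.

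**2. Does FPG mean fasting in this protocol?** Yes. Besides the glossary entry, the next monitoring rule (8.5.8, hyperglycemia) sets FPG thresholds and tells the investigator to verify that "Plasma glucose was actually measured in the fasting condition". A site that follows the protocol's own usage will read FPG the same way in 8.5.7.

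**3. Will readings at symptomatic events be fasting?** Not in general. Section 6.2.7 says "Fasting SMBG will be self-measured in the morning: daily if the patient is on insulin therapy", but those are scheduled tests. Under 8.5.7, patients who suspect hypoglycemia test promptly, whatever the hour. If waiting seems unsafe, they take sugar, milk or juice first and test afterwards; a reading taken then is not fasting.

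**4. Is an insulin reduction mandated anywhere else?** No. Section 8.6.4 requires Study Drug to be suspended after a first documented severe event, but leaves background medication to the investigator with the Medical Monitor. Section 8.5.8 concerns increases or rescue for high glucose.

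**5. Worked cases under the literal trigger**

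- Typical symptoms, afternoon reading of 52 mg/dL, not fasting: meets the definition (52 ≤ 70) and is recorded as an adverse event, but is not an FPG value, so no reduction is mandated.
- Typical symptoms, fasting reading of exactly 70 mg/dL: meets the definition (70 ≤ 70) but not the trigger (70 < 70 is false).
- Typical symptoms, fasting meter reading of 3.9 mmol/L: the unit pairs printed in 8.5.8 give the conversion.
  - 270/15.0 = 18.00, and 3.9 × 18.00 = 70.2 mg/dL
  - 240/13.3 = 18.05, and 3.9 × 18.05 = 70.4 mg/dL
  - 300/16.6 = 18.07, and 3.9 × 18.07 = 70.5 mg/dL

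  The reading meets the definition through its mmol/L limit but not the trigger. At 3.8 mmol/L the same factors give 68.4 to 68.7 mg/dL, which meets both if fasting.

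**6. Size of the mandated step.** At 200 U/day, the example of a high insulin requirement in the minor criteria of 5.1: 0.05 × 200 = 10 U/day and 0.15 × 200 = 30 U/day.

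**The case against.** The strongest reply is that the defined term governs, not the parenthesis. The sentence is about an episode of symptomatic documented hypoglycemia, which the same section defines. Section 8.5.8 lists fasting self-monitoring and FPG separately and uses FPG for the central laboratory value. Applied that strictly, the insulin rule would hardly ever fire for an event at home, which would defeat its purpose. So FPG may simply be loose wording. This reading is reasonable, and it limits the severity. It does not make the text right: the only compulsory insulin reduction should not depend on a charitable reading.

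The safety consequence is also limited, and this stands. Whenever a patient presents with symptoms, 8.5.7 requires the investigator to confirm glucose and treat. Glucometer printouts and episodes are reviewed at every clinic visit (6.2.7). Insulin is not among the drugs whose doses 8.10.1 says to leave unadjusted, so a voluntary reduction is open. Severe events have their own rule without a fasting condition. Only compulsory versus discretionary reduction is at stake, and the protocol accepts discretion elsewhere, including for background medication after a severe event.

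The 3.9 mmol/L example deserves less weight. Converted, the reading also exceeds the definition's own 70 mg/dL and qualifies only through the rounded mmol/L figure, so it partly reflects rounding. The clean boundary case is exactly 70 mg/dL. Likewise, 10 to 30 U/day is the size of the step, not the frequency of the problem.

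Finally, the documents do not say whether a fasting limit was intended, and a broader trigger would compel reductions after events with a one-off cause. That is a real but small cost. Against a deliberate fasting limit, Amendment 4 gives as its rationale guidance for symptomatic documented hypoglycemia and mentions no fasting restriction.

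**Conclusion.** The concern holds, at minor severity. The trigger in the current text of 8.5.7 is narrower than the definition of the event it names, in both measurement condition and inequality. Read literally, symptomatic non-fasting events, and fasting readings of exactly 70 mg/dL, fall outside the only mandatory insulin reduction.

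This rests on giving FPG its glossary meaning. Under the looser reading the gap closes, but the wording still permits two practices. The documents give neither the number of hypoglycemic events nor the share that are non-fasting, so no frequency is claimed. No efficacy endpoint or analysis population is defined by this trigger; SAP 3.7.9 only summarizes changes in antidiabetic medication.

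**What to change.** In the action paragraph of Protocol 8.5.7, replace the parenthesis with: measured plasma glucose ≤ 70 mg/dL (≤ 3.9 mmol/L), fasting or not. This is the definition already used in 6.2.7 and earlier in 8.5.7. It also supplies the missing mmol/L value, which is useful because 3.2 places the study at centers worldwide.

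The cost is one line of protocol wording, with no extra data or visits. The downside is somewhat more mandated reductions of 5 to 15%, including after events explained by a missed meal or unusual activity, which 8.5.7 itself recognizes as contributory factors.

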### **8.5.8 Monitoring Rule for Documented Hyperglycemia**

Routine fasting SMBG and central lab alerts on FPG (and HbA1c after Week 12) are set up to ensure that glycemic parameters remain under predefined thresholds values. If one fasting SMBG value exceeds the specific glycemic limit on 1 day, the patient checks it again during the 2 following days. If all the values in 3 consecutive days exceed the specific limit, the patient should contact the Investigator and a central laboratory FPG measurement (and HbA1c after Week 12) is performed.

The threshold values are defined as follows, depending on study period:

- From Baseline visit to Week 12 (including value at Week 12) of Randomized Treatment period or OLE period:
  - FPG > 300 mg/dL (16.6 mmol/L)
- From Week 12 to Week 24 (including value at Week 24) of Randomized Treatment period or OLE period:
  - FPG > 270 mg/dL (15.0 mmol/L) or
  - HbA1c > 9.5% (for patients with Baseline HbA1c < 8%) and HbA1c increase of more than 1.5% from Baseline (for patients with Baseline HbA1c ≥ 8%)
- From Week 24 up to Week 52 of Randomized Treatment period or OLE period:
  - FPG > 240 mg/dL (13.3 mmol/L) or
  - HbA1c > 9.5% (for patients with Baseline HbA1c < 8%) and HbA1c increase of more than 1.5% from Baseline (for patients with Baseline HbA1c ≥ 8%)

In case of FPG/HbA1c above the threshold values, the Investigator should ensure that no reasonable explanation exists for insufficient glucose control and in particular that:

- Plasma glucose was actually measured in the fasting condition
- Absence of intercurrent disease which may jeopardize glycemic control. In case of an emergency (e.g., surgery, infection), the Investigator can take appropriate measures for glycemic control. If the measure does not exceed 7 days, then it will not be considered a rescue. If the measure lasts beyond 7 days then it will be treated as a rescue
- Compliance to treatment is appropriate
- Compliance to diet and lifestyle is appropriate

If any of the above can reasonably explain the insufficient glycemic control, the Investigator should undertake appropriate action, i.e.:

- Investigation and treatment of intercurrent disease (to be reported in AE/concomitant medication parts of the eCRF)
- Stress on the absolute need to be compliant to treatment

- Organize a specific interview with a Registered Dietician or other qualified nutrition professional and stress on the absolute need to be compliant to diet and lifestyle recommendations
- Schedule a FPG/HbA1c assessment at the next visit

If none from the above-mentioned reasons can be found, or if appropriate action fails to decrease FPG/HbA1c under the threshold values, an increase in current medication or the addition of new anti-diabetic rescue medication may be introduced at Investigator discretion and according to local guidelines. Investigators should minimize changes prior to the primary endpoint, when possible. All adjustments to medication should be captured on the concomitant medication CRF and/or electronic diary.

All assessments for primary and secondary efficacy and safety parameters planned in final primary endpoint assessment visit should be performed before adding the rescue medication. Then the patient continues the study treatment and stays in the study in order to collect safety information. The planned visits and assessments should occur until the last scheduled visit. (See more details in [Appendix A](#)).

Note: After Study Drug discontinuation any treatments are permitted, as deemed necessary by the Investigator.

### **8.5.9      *Acute Pancreatitis***

If a patient has an episode of acute pancreatitis, dosing with Study Drug should be suspended temporarily until the patient is clinically stable. The suitability of the patient for continued dosing and the need for any modification to the treatment schedule (refer to [Section 8.7](#)) will be determined by the Investigator in consultation with the Study Medical Monitor.

## **8.6      *Stopping Rules***

For the purposes of stopping rules, baseline is defined as the average of Day 1 pre-dose assessment and the last measurement prior to Day 1.

### **8.6.1      *Stopping Rules for Liver Chemistry Elevations***

In the event of confirmed laboratory results meeting the following criteria, **and the event is without an alternative explanation as discussed with the Sponsor Medical Monitor**, dosing of a patient with Study Drug will be stopped permanently:

1. ALT or AST  $> 8 \times$  ULN, which is confirmed
2. ALT or AST  $> 5 \times$  ULN, which is confirmed and persists for  $\geq 2$  weeks
3. ALT or AST  $> 3 \times$  ULN (or the greater of 2 x Baseline value or 3 x ULN if the Baseline value was  $>$  ULN), which is confirmed **and** total bilirubin  $> 2 \times$  ULN or INR  $> 1.5$
4. ALT or AST  $> 3 \times$  ULN (or the greater of 2 x Baseline value or 3 x ULN if the Baseline value was  $>$  ULN), which is confirmed, and the new appearance (i.e., onset coincides with the changes in hepatic enzymes) of fatigue, nausea, vomiting, right upper quadrant pain or tenderness, fever, rash, or eosinophilia ( $>$  ULN) felt by the Investigator to be potentially related to hepatic inflammation

### **8.6.2 Stopping Rules for Renal Function Test Results**

In the event of persistent changes that are observed over 2 consecutive weeks, for any of the criteria below, dosing of a patient with Study Drug may be stopped temporarily:

1. Quantitative total urine protein measurement of  $> 3.5$  g/24 hours
2. Estimated creatinine clearance calculated according to the formula of Cockcroft and Gault  $\leq 40$  mL/min that is confirmed by a 24-hour urine collection

The possible dosing re-initiation or follow-up schedule for any events meeting either of these criteria will be determined by the Investigator **in consultation with** the Sponsor Medical Monitor or designee.

